7.9.3 Vital Signs and Other Physical Findings

Vital signs will be summarized by treatment group using descriptive statistics. For each vital sign, the baseline and final observations will be presented by treatment group. Additionally, the largest absolute change from baseline for systolic blood pressure and diastolic blood pressure, the highest value of pulse rate, and the largest absolute change in respiration rate will be summarized. Descriptive statistics will be calculated for the observed values as well as the change from baseline values.

A table of frequencies of vital sign abnormalities of interest that occur after baseline as defined in [Appendix Table 4](#) will be generated by treatment. The number and percentage of patients experiencing the abnormality as well as the total number of abnormalities will be presented. All vital sign values with an abnormality of interest will be listed.

Abnormal physical examination results will be listed.

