f Vital signs include blood pressure, heart rate, respiration, and oral temperature. On infusion days, vital signs will be measured 30 minutes prior to infusion and 5, 30, and 60 minutes after the end of the infusion. Vital signs should be collected as close to or at the exact indicated times as possible.

Predose sample only: On Week 1, a single blood sample will be taken within 2 hours prior to the start of the administration of the first dose.

Both predose and postdose samples: Both predose and postdose samples will be taken on Weeks 40 and 48 as follows: within 2 hours prior to the start of the infusion and approximately 5 to 10 minutes, 1 to 2 hours, and 2 to 4 hours after the completion of the infusion. An additional sample will be taken at Week 48 at the end of the infusion prior to flushing the infusion line.

Postdose samples only: On Weeks 8, 16, 24, and 32, a postdose sample will be taken approximately 5 to 10 minutes after the completion of the infusion (the approximate time of postdosing maximum plasma concentration for eteplirsen). Additional postdose samples will be taken at Weeks 8 and 24 at approximately 1 to 2 hours after the completion of the infusion. The 6MWT and NSAA will be performed on 2 consecutive days and may require 2-night overnight stays. Pulse will be obtained prior to and immediately after the 6MWT.

ECG and ECHO may be performed on either day of the specified 2-day visits during the treatment period.

mProcedure is only applicable for patients who qualify for the treated group and will occur at the surgical unit (SU). Upon qualification for the study during the Baseline visit, patients in the treated group will be randomized to 1 of 4 biopsy groups according to this muscle biopsy schedule: 1) biopsy at Baseline and Week 24, 2) biopsy at Baseline and Week 48, 3) biopsy at Baseline and Week 72, or 4) biopsy at Baseline and Week 96. The biopsies at Weeks 24, 48, 72, and 96 must occur within 2 weeks after the specified visit, after the clinical evaluation, and at least 48 hours after the most recent infusion.

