a Patients may continue in the safety extension for up to 48 weeks, until the product is commercially available or until they can transition into a separate eteplirsen study.

b Early termination assessments are the same as Week 144 assessments.

c Full physical examination: general appearance, head, eyes, ears, nose, and throat (HEENT), heart, chest, abdomen, skin, lymph nodes, extremities, musculoskeletal, and neurological systems.

d Vital signs include blood pressure, heart rate, respiration, and oral temperature. On infusion days, vital signs will be measured prior to infusion and approximately 5 and 30 minutes after the end of the infusion. If the patient has not experienced an infusion reaction after the first year of treatment, vital signs may be reduced to pre-infusion and 30 minutes after the end of the infusion.

Table 5: Schedule of Events for Untreated Control Patients - Screening Through End of Study

Assessments	Up to	10 weeks	prior to Week 1ª				Olara		•. ah			
Study Period		ening p to -3w	Baseline -4w to Day -1&-2		(2-da	ay HS visi		rvation Po t Weeks 1		48, 72, an	nd 96)	
Week	1-day visit	2-day visit	2-day visit (3-5w after Screening at HS)	W1°	W4	W8	W12	W24	W36	W48	W72	W96/ ET ^b
Informed consent for screening at local site	X											
Informed consent for screening at HS (if different from local site)		HS										
Informed consent to participate as a control patient (no consent form needed at W12 if local is same as HS)				X			HS					
Assess inclusion/exclusion criteria	X	HS	HS									
Confirm eligibility ^d			X	X								
Medical history	X											
Full physical examination ^e	X			X	X		X	X	X	X	X	X
Brief physical examination ^e						X						
Vital signs ^f	X		HS	X	X	X	X	X	X	X	X	X
Weight	X			X	X	X	X	X	X	X	X	X
Safety laboratory assessments ^g	X ^h			$X^{h,i}$	X	X	X	X	X	X	X	X

Table 5: Schedule of Events for Untreated Control Patients - Screening Through End of Study, continued

Assessments	Up to	10 weeks	prior to Week 1ª				Ohga	rvation P	out o db				
Study Period		ening p to -3w	Baseline -4w to Day -1&-2		(2-da	ny HS visi	ts occur a			48, 72, an	d 96)		
Week	1-day visit	2-day visit	2-day visit (3-5w after Screening at HS)	W1°	W4	W8	W12	W24	W36	W48	W72	W96/ ET ^b	
Immunogenicity				Xi	X	X	X	X	X	X	X	X	
CCI													
Whole blood for DMD genotyping	X												
CCI													
Height (and ulnar length at HS visits)	X		HS				HS	HS	HS	HS	HS	HS	
6MWT ^j		HS	HS				HS	HS	HS	HS	HS	HS	
NSAA ^j			HS				HS	HS	HS	HS	HS	HS	
CCI													

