9.3. Treatments Administered

Eligible patients who have an out-of-frame deletion that may be treated by skipping exon 51 will receive 30 mg/kg/week eteplirsen as an IV infusion for up to 96 weeks (treated group). Eligible patients who have out-of-frame deletions that are not amenable to treatment by skipping exon 51 will remain on their existing standard of care but will not receive eteplirsen throughout the study (untreated control group).

For the treated group, the following guidelines for the timing of dosing should be followed throughout the study:

1. Patients should receive eteplirsen once every 7 days starting on Study Day 1. A window of ±3 days from the scheduled dose is acceptable after the first infusion. For visits where safety assessments are not being collected, optional in-home administration of eteplirsen by a visiting nurse may be available after Week 25. For in-home dosing, additional instructions will be provided in a separate manual to the visiting nurse.

- 2. Patients may not receive 2 separate doses of eteplirsen within the same 60-hour period.
- 3. The medical monitor should be contacted in the event of a missed dose.

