10.2.3. Weekly Infusions (Weeks 1-96) (for the treated group only)

At Local Sites:

- Vital signs, including include blood pressure, heart rate, respiration, and oral temperature. Vital signs will be measured 30 minutes prior to the start of the infusion and 5, 30, and 60 minutes after the end of the infusion. If the patient has not experienced an infusion reaction after the first year of treatment, vital signs may be reduced to pre-infusion and 30 minutes after the end of the infusion. Vital signs should be collected as close to or at the exact indicated times as possible.
- Eteplirsen will be administered via an IV infusion. Patients should be closely monitored for at least 1 hour following the completion of all infusions. It is recommended that a topical anesthetic cream (e.g., lidocaine 2.5%, prilocaine 2.5% or LMX4 cream) be applied prior to infusions. Refer to the Pharmacy Manual for specific instructions regarding IP reconstitution with normal saline.

10.2.4. Additional Procedures for Week 1

The assessments below should occur during a single day at a patient's Local Site.

- Full physical examination, including examination of general appearance, HEENT, heart, chest, abdomen, skin, lymph nodes, extremities, musculoskeletal, and neurological systems
- Vital signs
- Weight (This measurement will be used to calculate the eteplirsen dose for patients in the treated group.)
- Safety laboratory assessments, including chemistry, hematology, coagulation, and urinalysis
- Immunogenicity
- At a subset of sites for patients in the treated group, 1 blood sample for assessing plasma drug concentrations (PK) will be taken within 2 hours prior to the start of the first infusion of eteplirsen.

10.2.5. Additional Procedures for Week 4

Assessments should occur during a single day at the patient's Local Site.

- Full physical examination, including examination of general appearance, HEENT, heart, chest, abdomen, skin, lymph nodes, extremities, musculoskeletal, and neurological systems
- Vital signs
- Weight
- Safety laboratory assessments, including chemistry, hematology, coagulation, and urinalysis
- Immunogenicity

10.2.6. Additional Procedures for Week 8

Assessments should occur during a single day at the patient's Local Site.

- Brief physical examination, including examination of general appearance, HEENT, heart, chest, abdomen, and skin
- Vital signs

- Weight
- Safety laboratory assessments, including chemistry, hematology, coagulation, and urinalysis

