6.7. Definitions and Terminology

Day 1

Day 1 will be defined as the date of the first eteplirsen dosing for eteplirsen-treated patients, or the Week 1 visit date for untreated control patients.

Study Day

Study day will be defined as Event Date – Day 1 + 1.

Duration on Study

Duration on study will be calculated as the duration in weeks from Day 1 to the date of study completion/discontinuation as recorded on the END OF STUDY eCRF (if completed) or the date of the last study assessment or procedure.

Duration on Eteplirsen

Duration on eteplirsen will be calculated as the duration in weeks from Day 1 to the date of the last eteplirsen administration as recorded on the STUDY DRUG ADMINISTRATION eCRF plus 6 days (ie, [last dose – first dose date + 1 + 6]/7).

Duration in weeks calculated above will be then categorized to 1 of the following intervals: <24, 24 to <48, 48 to <72, 72 to <96, or ≥ 96 .

Planned Dose and Overdose

The body weight-based planned dose was calculated based on most recent weight of previous visits. When calculating the planned dose, the body weight is rounded to a single decimal using conventional rounding rules. While in preparing actual dose, an unconventional rule is applied for calculating the volume of the concentrated drug (50 mg/mL) in milliliter. Any volume of 0.1 or above is rounded up (eg 25.14 mL is rounded up to 26 mL) and any volume below 0.1 is rounded down (eg 25.09 mL is round up to 25 mL). The overdose is defined as any actual dose $>10\%$ above the planned body weight-based dose.

Baseline Visit and Baseline value

Baseline visit will be considered the last visit prior to the initiation of eteplirsen for eteplirsen-treated patients, or the last visit on or before the Week 1 visit for untreated control patients. For any assessment that is taken on 2 consecutive days at baseline visit the base visit (ie, 6MWT, NSAA items and total score, FVC % predicted), the average value will be considered as the baseline value. If the assessment is taken or available only on 1 day at baseline visit, then the value on that day will be used as baseline value.

Change from Baseline

Change from Baseline will be calculated as follows:

$$\text{Change from Baseline} = \text{Post-Baseline Value} - \text{Baseline Value}$$

Percent Change from Baseline

Percent change from Baseline will be calculated as follows:

$$\text{Percent change from Baseline} = (\text{Change from Baseline} / \text{Baseline Value}) * 100$$

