- TEAEs reported in $\geq 10\%$ of patients in any treatment group (upon examination of the actual data, different cut-off points may be used to examine the incidence of these AEs if it is deemed appropriate)
- TEAEs reported in $\geq 2\%$ of patients in the active treatment group (and greater than untreated group)

The following listings will be produced:

- Listing of non-TEAEs
- Listing of TEAEs
- Listing of TEAEs leading to discontinuation of study drug
- Listing of TEAEs leading to withdrawal from study

Listings will include all data with an indicator for treatment period for each record when the event occurred.

Serious Adverse Events and Deaths

The following summary tables will be produced:

- treatment-emergent nonserious AEs
- treatment-emergent SAEs
- treatment-related, treatment-emergent SAEs
- deaths and AEs resulting in death
- AEs leading to study drug discontinuation by SOC and PT

The following listings will be produced:

- Listing of all AEs
- Listing of AEs leading to discontinuation
- Listing of SAEs (including pre-dosing SAEs)
- Listing of death
- Listing of SAEs that occurred prior to the initiation of study drug or after 28 days post-last dose will be excluded from the tables but will be included in the listing at the start date/time of the AE.
- Listing of AEs related to study procedure by SOC and PT

Listings will include all data with an indicator for treatment period for each record when the event occurred.

A summary of deaths and reasons for deaths will be presented by Analysis period and treatment group. A patient-level listing will be provided.

Adverse Events of Special Interest

Summaries of AEs of special interest will be summarized by SOC and PT. All standardised MedDRA Queries ([SMQs]) listed below will include broad and narrow terms. The AESI are:

- hypersensitivity (hypersensitivity SMQ)
- renal toxicity (acute renal failure SMQ)
- infusion-related reaction (IRR) (AEs occurring within 24 hours of the start of any infusion [including events occurring on the same date as an infusion where infusion start time or AE onset time was not reported])

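### The SAP plans no change from the pre-infusion to the post-infusion vital-sign reading and no summary by time after infusion, although the protocol schedules readings around each infusion

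*SAP*

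**What the plan says.** **Collection.** The footnotes to Tables 2 and 3 in Protocol Section 2 state for infusion days that "vital signs will be measured 30 minutes prior to infusion and 5, 30, and 60 minutes after the end of the infusion". Section 10.2.3 repeats this for the weekly infusions in Weeks 1 to 96. For a boy without an infusion reaction in the first year, "vital signs may be reduced to pre-infusion and 30 minutes after the end of the infusion". In the safety extension (Table 4) there is no 60-minute reading: "vital signs will be measured prior to infusion and approximately 5 and 30 minutes after the end of the infusion". Dosing is weekly: "Patients should receive eteplirsen once every 7 days starting on Study Day 1" (Section 9.3).

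**Analysis.** SAP 6.7 sets the reference: "Baseline visit will be considered the last visit prior to the initiation of eteplirsen for eteplirsen-treated patients". SAP 7.9.3 then plans:
- for each vital sign, "For each vital sign, the baseline and final observations will be presented by treatment group";
- "the largest absolute change from baseline for systolic blood pressure and diastolic blood pressure";
- the highest pulse rate, and the largest absolute change in respiration rate (reference not named);
- patients with, and total numbers of, post-baseline values outside Appendix Table 4.

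SAP 8.1 drops by-visit summaries and sends by-visit results to listings. Protocol 13.10.2.2 also plans only change from Baseline to each visit.

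**The named harm.** SAP 7.9.1 makes this an adverse event of special interest: "infusion-related reaction (IRR) (AEs occurring within 24 hours of the start of any infusion".

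**The concern.** Readings before and at set minutes after an infusion allow each boy to serve as his own reference on the same day. That removes day-to-day variation and growth over 96 weeks. No planned table uses the readings in this way.

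The route through infusion-related reactions depends on someone reporting an event. Under Protocol 11.2.1, test abnormalities count as adverse events when they alter medical care. A modest, symptomless but consistent change in blood pressure or pulse after infusion need never become one.

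The untreated arm has no infusions and far fewer readings. Extremes and abnormality counts will therefore differ between arms partly through the number of readings alone. The largest absolute change also discards direction, so falls and rises are merged.

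**Working it through.** The documents give no variance, power or error rate for vital signs, so there is no plan figure to reproduce. The reading counts come from the schedules; the rest is illustration.

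**Step 1: readings per boy, Week 1 to Week 96.**
- Treated, full schedule: 96 × 4 = 384.
- Treated, reduced after year 1: 52 × 4 + 44 × 2 = 296.
- Narrowest count, using only the 13 visit columns of Table 2 for Weeks 1 to 48 and two readings for each of the 48 later infusions: 13 × 4 + 48 × 2 = 148, with 13 × 3 + 48 = 87 same-day post/pre pairs.
- Control, after Week 1 (Table 5): Weeks 4, 8, 12, 24, 36, 48, 72 and 96, that is 8 visits.

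The treated counts fall by one if the Week 1 pre-infusion reading serves as Baseline.

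**Step 2: noise in the two kinds of change.** Assume each systolic reading is the boy's level plus a day-to-day deviation (SD d) and a within-day deviation (SD w), with one Baseline reading.
- One change from Baseline: SD = √(2(d² + w²)).
- One same-day change: SD = √2 × w.
- A boy's mean change over 96 infusions at one post-infusion time: from Baseline, √((d² + w²)(1 + 1/96)); from the same-day reading, √(2w²/96).

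For d = 8, w = 5: √178 = 13.3; √2 × 5 = 7.1; √(89 × 1.0104) = 9.5; √(50/96) = 0.72.

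| d / w (mmHg, assumed) | One change, Baseline | One change, same day | Mean change, Baseline | Mean change, same day |
|---|---|---|---|---|
| 6 / 4 | 10.2 | 5.7 | 7.2 | 0.58 |
| 8 / 5 | 13.3 | 7.1 | 9.5 | 0.72 |
| 10 / 6 | 16.5 | 8.5 | 11.7 | 0.87 |

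Growth would add to the Baseline columns only.

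**Step 3: response of the planned blood pressure extreme.** Simulated mean of the largest absolute change from Baseline, with a true 5 mmHg rise at the 5-minute reading of every infusion:

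| d / w | Control, 8 readings, no effect | Treated, 384 readings, no effect | Treated, with rise | Shift |
|---|---|---|---|---|
| 6 / 4 | 16.4 | 26.7 | 27.8 | 1.1 |
| 8 / 5 | 21.6 | 34.9 | 35.7 | 0.8 |
| 10 / 6 | 26.8 | 42.7 | 43.9 | 1.2 |

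With no drug effect the arms already differ by 10.3, 13.3 and 15.9 mmHg, from reading count alone.

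On the narrowest schedule (148 readings), with 2 mmHg/year drift and a 5 mmHg fall at every post-infusion reading, the figures move from 25.1 to 26.1, 32.3 to 33.3 and 40.2 to 40.8. The SD between boys is 5 to 8. The mean same-day change moves from 0.0 to -5.0 each time (SD between boys 0.7 to 1.1).

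**Step 4: where the planned output does respond.** With d = 8, w = 5 and the 148-reading schedule:
- One isolated 40 mmHg fall per boy raises the largest absolute change from about 32 to above 40 mmHg. The mean same-day change barely moves: -40/87 = -0.46.
- With a consistent 5 mmHg fall and an assumed between-boy SD of 8, readings below 90 mmHg per boy rise from about 24 to 34 if mean systolic pressure is 100, and from about 2 to 4 if it is 115. As planned, those counts do not separate pre- from post-infusion readings.

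**The case against.** A reader might infer that every reading is compared only with the study Baseline, so that an infusion effect is lost or cannot be shown. The documents do not support that:
- Appendix Table 4 judges blood pressure, pulse, respiration and temperature against fixed limits, and pulse is summarised as its highest value.
- Values outside the limits are counted and listed, and by-visit results are listed.
- Reactions reported within 24 hours of an infusion enter the special-interest analysis, with physician review and separate tables.
- Step 4 shows that isolated large falls move the planned extreme strongly, and that a consistent fall raises the count of low readings.

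Two further cautions are fair. No text says that the timed readings exist to estimate an infusion effect. They sit beside the one-hour post-infusion observation and suit bedside monitoring equally well. Nor does the SAP state that pre- and post-infusion readings are pooled; it is silent on which same-day reading is the visit value or the final observation. The safety analyses are declared descriptive, and SAP 8.1 openly declares the reduced summaries.

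All of this limits the claim without removing it. Listings are not a summary, reported events depend on reporting, and counts that are not split by timing cannot be attributed to the infusion.

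**Conclusion.** The point holds in a limited form. The SAP plans no same-day pre-to-post-infusion change and no summary by time after infusion. A consistent infusion-related shift that is not reported as an adverse event would not be summarised or attributable to the infusion. Comparison with controls does not help, because 8 scheduled visits stand against 296 to 384 readings per treated boy (148 on the narrowest count).

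In the settings tested, a consistent 5 mmHg shift moves the mean largest absolute change from Baseline by 0.6 to 1.2 mmHg, against the full 5 mmHg in the mean same-day change. The reading counts come from the schedules and assume full attendance. The SDs, drift, mean pressures and effect sizes are assumptions, so these results show direction and rough scale only. They do not show that the planned output would miss every infusion effect.

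**What to change.** In SAP 7.9.3, for eteplirsen-treated patients:
- Add the signed change from the same-day pre-infusion reading to each available post-infusion time (5, 30 and 60 minutes; 5 and 30 in the extension) for blood pressure, pulse, respiration and temperature, summarised by time point.
- Add each patient's largest same-day fall and largest same-day rise, because the mean change is insensitive to isolated events.
- Split the Appendix Table 4 counts into pre- and post-infusion readings.
- State which same-day reading is the visit value and which is the final observation, and name the reference for the respiration change.

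Keep the planned summaries of change from Baseline.

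Separately, Protocol 10.2 says that assessments on an infusion day are completed before the infusion, except postdose pharmacokinetic draws. The footnotes to Tables 2 and 3 and Section 10.2.3 schedule vital signs after it. These passages must be reconciled.

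The analysis changes cost SAP wording and one or two extra tables from data already scheduled for collection. They alter no dosing or monitoring rule.

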Procedure is only applicable for patients who qualify for the treated group and will occur at the surgical unit (SU). Upon qualification for the study during the Baseline visit, patients in the treated group will be randomized to 1 of 4 biopsy groups according to this muscle biopsy schedule: 1) biopsy at Baseline and Week 24, 2) biopsy at Baseline and Week 48, 3) biopsy at Baseline and Week 72, or 4) biopsy at Baseline and Week 96. The biopsies at Weeks 24, 48, 72, and 96 must occur within 2 weeks after the specified visit, after the clinical evaluation, and at least 48 hours after the most recent infusion.

j Eteplirsen will be administered by IV infusion. Patients should be closely monitored for at least 1 hour following the completion of all infusions. It is recommended that a topical anesthetic cream (e.g., lidocaine 2.5%, prilocaine 2.5% or LMX4 cream) be applied prior to infusions. Optional in-home administration of eteplirsen by a visiting nurse may be available after Week 25 for visits where safety assessments are not being collected.

Table 4: Schedule of Events for Patients in the Treated Group – Safety Extension (Week 97 through End of Study)

Assessments			Safety Extension ^a			End of Study						
Study Period						a a saaa ay						
Week	Week 97	W108	W120	W132	W144	W148/ET ^b						
Full physical examination ^c			X		X	X						
Vital signs ^d		Weekly Every 4 weeks										
Weight				X								
Safety laboratory assessments ^e			X		X	X						
Eteplirsen infusion ^f	(to	Once Weekly ± 3 days (to be scheduled based on Week 1 infusion date) at Local Site										
Conmed/therapy		Continuous										
AE assessment			Continuo	ous								

X = Local Site

- e Safety laboratory assessments include chemistry, hematology, coagulation, and urinalysis.
- f Eteplirsen will be administered by IV infusion. Patients should be closely monitored for at least 1 hour following the completion of all infusions. It is recommended that a topical anesthetic cream (e.g., lidocaine 2.5%, prilocaine 2.5% or LMX4 cream) be applied prior to infusions. Patients who discontinue treatment with eteplirsen will have an End of Study visit (see W148 procedures) 4 weeks after their last infusion. Optional in-home administration of eteplirsen by a visiting nurse may be available for visits where safety assessments are not being collected.

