6.6. Presentations Over Time

For endpoints that are collected serially over time (eg, 6MWT distance, clinical laboratory tests), assessments/test values will be assigned to a specific time point (eg, study week) based upon the electronic case report form (eCRF) page on which the assessments/test values were reported.

For an efficacy endpoint, an unscheduled assessment may be used in the summary by time point if the unscheduled assessment was within 2 weeks of a missing scheduled assessment.

For safety endpoints, unscheduled assessments will not be included in the summary by time point.

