8. CHANGES IN PLANNED ANALYSES

8.1. Changes from Protocol-Planned Analyses

The following changes were made compared to the protocol-planned analyses:

- Comparisons between the eteplirsen-treated group and the untreated control group will not be performed due to the expected very small number of patients in the untreated control group and the differences in the populations between the treated and untreated groups. No hypothesis test, no p-value and no inferential statistics will be made for comparison of eteplirsen treated patients and untreated patients
- CCI [REDACTED]
- The observed values and changes from baseline for clinical laboratory assessments, vital signs and ECG will only be summarized for baseline, the last visit (final observation) and the highest/lowest values. All clinical laboratory assessments, vital signs and ECG results by visit will be in data listing.
- Renamed “predefined change abnormal” to “predefined markedly abnormal” for clinical laboratory tests and other safety endpoints.
- CCI [REDACTED]

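### SAP 7.9.3 sets vital-sign extremes and abnormality counts side by side although treated boys have at least 24 scheduled readings to Week 96 and controls 8, so the treated column runs higher with no drug effect

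*SAP*

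**What the plan says.** SAP 7.9.3 presents vital signs by treatment group. Besides baseline and final observations it summarises "the largest absolute change from baseline for systolic blood pressure and diastolic blood pressure, the highest value of pulse rate". Respiration rate is handled like blood pressure, by its greatest shift in either direction. A second table counts the Appendix Table 4 abnormalities arising after baseline: "The number and percentage of patients experiencing the abnormality as well as the total number of abnormalities will be presented". The section sets no shared-visit rule, no pre-infusion rule, no Week 96 cut and no per-reading denominator.

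Two other SAP passages bear on which readings enter. Section 8.1 drops the protocol's by-visit summaries: laboratory, vital-sign and ECG values "will only be summarized for baseline, the last visit (final observation) and the highest/lowest values", and by-visit results go to listings. Section 6.6 says: "For safety endpoints, unscheduled assessments will not be included in the summary by time point". That rule covers by-time-point summaries only, and the extra treated readings are scheduled ones anyway.

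On how often vital signs are taken, the protocol says the following.

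- Table 5 (controls): Weeks 4, 8, 12, 24, 36, 48, 72 and 96 after Week 1.
- Table 2 (treated, to Week 48): ticks every 4 weeks. The vital-signs footnote adds: "On infusion days, vital signs will be measured 30 minutes prior to infusion", with three further readings after the infusion.
- Table 3 (treated, Weeks 49 to 96): weekly.
- Section 10.2.3 (weekly infusions, Weeks 1 to 96): "measured 30 minutes prior to the start of the infusion and 5, 30, and 60 minutes after the end of the infusion", reducible to two readings after a reaction-free first year.
- Table 3, infusion footnote: home infusion "may be available after Week 25 for visits where safety assessments are not being collected".
- Table 4 (extension, treated only): "vital signs will be measured prior to infusion and approximately 5 and 30 minutes after the end of the infusion".

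**The concern.** A maximum, a largest change, an ever-abnormal flag and a raw count all grow with the number of readings. If one arm is read at least three times as often, its column is higher even when the drug does nothing. SAP 7.9 presents all safety summaries by treatment group, so readers will see the two columns together. Once by-visit summaries are dropped, no planned vital-sign table compares the arms over the same set of repeated readings. The final-observation summary does not depend on reading count, but it does not correct the other tables. An excess in the treated column would be hard to interpret from these tables alone.

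**Working it through.** The plan states no figure on this point, so there is none to reproduce. The abnormality rates, correlations and standard deviations below are assumptions, shown as ranges.

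**1. Scheduled readings after the Week 1 pre-dose value, to Week 96**

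| Schedule | Count |
|---|---|
| Control (Table 5) | 8 |
| Treated, 4-weekly visits only, one reading each | 96/4 = 24 |
| Treated, Tables 2 and 3 as ticked, one per visit | 12 + 48 = 60 |
| Treated, 10.2.3 weekly, one per visit | 95 |
| Treated, Tables 2 and 3, all timed readings | 3 + 60×4 = 243; reduced after Week 52: 3 + 12×4 + 4×4 + 44×2 = 155 |
| Treated, 10.2.3, all timed readings | 96×4 − 1 = 383; reduced: 52×4 − 1 + 44×2 = 295 |

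The figure of 24 is the floor: it supposes that no other infusion day is recorded. Extension readings come on top. All eight control visits are also treated visits.

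**2. Total abnormalities.** The expected count per completer is n×p, so the ratio is n/8 whatever the rate p or the correlation: 24/8 = 3, 60/8 = 7.5, 95/8 = 11.9. Raw totals also scale with arm size (planned 70 + 10 = 80 treated, 20 + 10 = 30 control). At an assumed p = 1%, control is 30×8×0.01 = 2.4 and treated is 80×24×0.01 = 19.2.

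**3. Percentage ever abnormal.** I used a random-intercept probit: with c = Φ⁻¹(1−p) and within-boy correlation ρ, P(ever) = ∫ φ(b){1 − Φ[(c − √ρ·b)/√(1−ρ)]ⁿ} db, with the same p in both arms.

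| p | ρ | n = 8 | n = 24 | n = 60 | 24 v 8 | 60 v 8 |
|---|---|---|---|---|---|---|
| 0.1% | 0.5 | 0.69% | 1.68% | 3.22% | 2.44 | 4.69 |
| 0.1% | 0.9 | 0.32% | 0.51% | 0.71% | 1.58 | 2.18 |
| 0.5% | 0.5 | 3.06% | 6.68% | 11.44% | 2.18 | 3.73 |
| 0.5% | 0.9 | 1.41% | 2.09% | 2.75% | 1.48 | 1.94 |
| 5% | 0.5 | 21.91% | 36.51% | 49.47% | 1.67 | 2.26 |
| 5% | 0.9 | 10.86% | 14.25% | 17.11% | 1.31 | 1.57 |
| 30% | 0.5 | 71.81% | 85.92% | 92.58% | 1.20 | 1.29 |
| 30% | 0.9 | 46.92% | 53.77% | 58.61% | 1.15 | 1.25 |

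**4. Highest pulse.** The expected maximum of n independent standard normal deviations is 1.424, 1.948 and 2.319 for n = 8, 24 and 60. The gap over control is 0.52 or 0.90 within-boy SDs. At an assumed SD of 8 to 12 beats/min that is 4–6 or 7–11 beats/min.

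**5. Weight and laboratory tests.** Weight is scheduled at 24 treated visits against 8. Laboratory visits match to Week 96 (8 v 8). Weeks 120, 144 and 148 make it 11 v 8 if the extension enters.

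**6. Adverse events (secondary).** SAP 7.9.1 includes a table of events in at least 2% of treated patients and more frequent than in controls. With P(event) = 1 − exp(−λt), 80 v 30 patients, no drug effect and an assumed 2 to 20 events per 100 patient-years, a null event meets this rule with probability:

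- 0.48–0.50 at equal follow-up;
- 0.50–0.54 at 96 + 4 = 100 v 96 weeks;
- 0.60–0.75 at 124 v 96;
- 0.68–0.89 if every treated boy reaches 96 + 48 + 4 = 148 weeks;
- 0.51–0.82 at 96 weeks with an assumed 20–60% control dropout.

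**7. After the fix.** Eight readings per completer in each arm give equal ever-abnormal percentages under no effect. Raw totals at p = 1% would still be 80×8×0.01 = 6.4 against 2.4, a ratio of 2.7, so they need a denominator; per 100 readings both are 1.0. At p = 0.5%, ρ = 0.5 and 20–60% control dropout, ever abnormal is 3.1% against 2.9–2.4%, a small residue.

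**The case against.** - **Nothing rests on these columns.** SAP 6.3 and 8.1 rule out comparison of the arms, and SAP 7.9 makes safety descriptive. This stands, and it limits the weight of the point. It does not remove it, because the columns are still printed by arm and SAP 7.9.1 itself selects events more frequent than in controls.
- **Infusion effects have their own route.** Adverse events within 24 hours of an infusion are of special interest, medically reviewed, summarised and listed (SAP 7.9.1), and every vital-sign value meeting an abnormality criterion is listed. This stands. A reader might infer that oversampling would hide a real infusion effect altogether; the documents do not support that.
- **The size depends on assumptions.** This stands for the ever-abnormal percentage. A reader might reach for a large multiple: 383 readings at 0.1% and correlation 0.5 give about 13.6. That treats four readings around one infusion as exchangeable and takes the fullest schedule. Nor do the documents give a lower bound, since common abnormalities and high correlation bring the ratio close to 1. The direction and the count ratio need no such assumption.
- **The schedule conflict is partly layout.** Table 2 has columns only for nominal visits. Its footnote speaks of infusion days, which are weekly, and so agrees with 10.2.3 and Table 3. This stands. The home-infusion wording remains in tension with weekly vital signs, and the case-report forms that would settle which readings are captured are not in the documents.
- **Weight is different.** A reader might infer the same inflation for the criterion of at least 7% weight loss. No figure supports that: a sustained loss would also be seen at eight visits over the same 96 weeks.
- **Pulse around the walk test** is scheduled equally in both arms and would narrow the pulse gap if pooled with vital signs. The schedule lists vital signs as a separate row.

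**Conclusion.** The point holds as a modest presentation bias. With no drug effect, the SAP 7.9.3 extremes, ever-abnormal percentages and totals run higher in the treated column because treated boys are read more often. Expected total abnormalities per completer are at least 3 times control, assuming only scheduled attendance and a common rate per reading. For 24 against 8 readings the ever-abnormal ratio is about 1.15 to 2.4 over assumed rates of 0.1–30% and correlations of 0.5–0.9; for 60 against 8 it is about 1.25 to 4.7.

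It is not an error in a trial conclusion, and the bias runs against the drug. The adverse-event point is secondary: it is negligible without extension follow-up or control dropout. SAP 4.4.2 calls control dropout large, but the documents put a number on neither. The 148-week case is a ceiling, because the extension can end at commercial availability or transfer to another study.

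**What to change.** 1. Base side-by-side vital-sign extremes and abnormality tables on Weeks 4, 8, 12, 24, 36, 48, 72 and 96, using the pre-infusion reading for treated boys. Report all other infusion-day and extension readings in treated-only tables, so that no signal is lost.
2. Give total abnormalities per 100 readings, because raw totals also move with arm size and dropout.
3. Use the same shared visits for weight as a precaution; the size of any effect there is not shown.
4. Cut the side-by-side laboratory highest/lowest values and abnormality table at Week 96. SAP 7.9.2 already limits one laboratory shift summary to the treatment period.
5. Secondary: add adverse-event rates per patient-year through Week 96 and apply the more-frequent-than-control selection to them. In simulation with 0–60% control dropout, 46–53% of null events were then selected, so the tilt goes but the noise stays.
6. Reconcile protocol 10.2.3, Tables 2 and 3 with the Table 2 vital-signs footnote, and the home-infusion text on when vital signs are recorded. State in the SAP which readings enter.
7. Note differing contact frequency and control dropout as remaining limitations.

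The cost is a few extra tables, some SAP text and one protocol clarification. No new data are needed.
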